#### *P.1.2 Reimbursement*

Trial reimbursement is outlined in the Clinical Trial Agreement.

#### *P.1.3 Indemnification*

Indemnification will be done according to local laws.

#### *P.1.4 Subject confidentiality*

At all times throughout the trial confidentiality shall be observed by all parties involved. All information and data sent to parties involved in trial conduct concerning patients or their participation in this trial will be considered confidential. The patient identification number is to be recorded on all trial documents and will link the trial documents to the patient's name and medical record at the investigator's site. To maintain confidentiality, the patient's name or any other personal identifiers should not be recorded on any trial document other than the informed consent form.

## **R.2 List of Participating Investigational Centers**

The list of participating Investigational Centers will be provided under separate cover.

#### **R.4 Additional Records and Reports**

No additional records and/or reports, other than those previously described in this investigational plan or required by FDA, will be maintained for this clinical investigation.

## **R.5 Sample Case Report Forms**

Sample Case Report Forms (CRFs) will be provided under separate cover.

## R.6 Aortogram Acquisition Guidelines

The purpose of the acquisition guidelines is to increase consistency and effectiveness in reviewing the procedural aortograms.

### 1. Required aortogram:

- Index Procedure –TAVI

### 2. Required cine runs:

- Pre-procedure aortogram in a projection with 3 aortic cusps aligned (for comparison of final aortogram with pre-procedure aortogram)
- Final aortogram at least 10 minutes after TAVI implantation in the exact same projection as the pre-procedure aortogram (in order to measure depth of implantation and assess grade of aortic regurgitation)

**NOTE:** If the apex is not clearly visible in the final projection and in case of adequate renal function, in order to assess grade of AR, perform an additional final aortogram in RAO 30° with visualization of the left ventricle in long axis, including the apex.

### 3. Guidelines on how final aortogram after deployment of the valve should be performed:

- Use at least 20 ml of contrast, with an injection rate of 20 ml/sec
- Position the pigtail catheter in the upper third part of the frame
- Preferably use non-diluted contrast. 50%-diluted contrast is acceptable in case of renal insufficiency
- Use the angiographic projection with the three aortic cusps aligned in 1 plane:
  - Whenever available this optimal projection can be suggested by baseline MSCT exam
  - Pragmatic approach might be to use a shallow LAO or RAO projection, and adjust in a cranial or caudal position respectively to approach the optimal projection
- Confirm visualization of the left ventricular apex on the final aortogram
- Perform the final aortogram at least 10 minutes after deployment of the investigational TAVI device; include a time indication on the aortogram
- Use marker pigtail or provide the French-size of the pigtail catheter for calibration purpose

[figure not shown]
### 4. General imaging and recording procedures:

- Use a fixed table system and biplane x-ray equipment, if available
- Recommended resolution: 1024 x 1024 pixels
- Preferred acquisition speed: 25 frames/second
- One single cine run should have a duration of at least 5 heart beats
- The digital clock should be activated
- The maximum magnification factor should be applied during cine run without losing the image of the entire frame
- There should be no overlap of the frame with other catheters or electrodes
- Foreshortening of the frame should be avoided as much as possible
- Upload all images to InteleGRID (secure electronic system used for transferring images)

**5. Core lab analysis:**

The procedural aortograms may be analyzed by a core laboratory. Analysis would include:

- Grade of aortic regurgitation
- Depth of implantation

**Figure 1:** Example of depth of implantation measurement.

## R.7 Echocardiography Acquisition Guidelines

### 1. Scope of the document

These guidelines aim to increase consistency and effectiveness in collection and adjudication of echocardiography data of selected candidates for the SURTAVI trial. Optimal image acquisition, storage, and transmission will be described.

### 2. Protocol required echocardiograms

Transthoracic echocardiography is required at the following intervals:

Screening	- 45 days of Heart Team review
Post-Procedure OR Discharge	Between 24hrs post-procedure and hospital discharge (but no later than 7 days from post Index Procedure)
6 months	± 30 days
12 months	± 30 days
24 months	± 60 days
3,4,5 years	± 60 days

### 3. Four general rules for echocardiography recordings

3.1 Rule #1 for overall recordings: adhere STRICTLY to the PROTOCOL regarding:

- **number** and **order** of recordings as listed on the Table
- **do not perform measurements** on the echo recordings, except screening echo to be submitted for screening committee review (see measurements noted in section 4)
- at end of echo exam, export all required recordings in **DICOM** format and upload it to InteGRID
- only one **certified** echocardiographer (+ 1 replacement) is allowed to participate in the study, he/she should print his/her name, fill in contact details and sign the transmittal form

3.2 Rule #2 for Doppler recordings:

- Unless stated otherwise, all pulsed-wave and continuous-wave Doppler signals should be recorded at a **sweep speed of 50-100 mm/sec** (recording must contain minimum of three heartbeats) with optimized gain and filter setting, baseline position, and velocity range.

3.3 Rule #3 for apical 2D views (4-, 5-, 2-, and 3-Chamber views)

- pay attention to ultrasound sector **depth** and **gain** settings
- the aortic valve should be out of scan plane in the 4-CH view
- please avoid patient or transducer **motion** and record during **quite respiration** unless stated otherwise
- make sure the **entire LV myocardium** (including epicardium and apex) is recorded in the scan sector in particular at end-diastole
- make sure **Frame Rate** is more than 30Hz for 2D grey-scale and around 20Hz for colour Doppler aortic regurgitation

3.4 Rule #4 for EF calculation (apical 4-, 2-, and 3-Chamber views focused on LV)

- Record **3 runs** (run 1: 3 beats, run 2: 3 beats, run 3: 10 beats)

### 4. Data requirements

Participating centers in the SURTAVI study should obtain the appropriate Doppler and echocardiography recordings to document the following variables.

- Aortic annulus long-axis diameter in mid-systole (screening/baseline only)\*
- LVOT long axis diameter in mid-systole
- Sinus of Valsalva diameter (SOV) at end diastole (screening/baseline only)\*
- Sino-tubular junction diameter (STJ) at end diastole (screening/baseline only)\*
- Sinus of Valsalva height (SOVH) at end-diastole (screening/baseline only)\*
- Max aortic valve velocity (V2) by CW Doppler
- Velocity time integral (VTI) across aortic valve by CW Doppler
- Mean gradient across aortic valve (MGV2) by CW Doppler\*
- Peak LVOT velocity (V1) by PW Doppler
- Velocity Ratio (V1 / V2)
- Velocity time integral (VTI) of LVOT velocity by PW Doppler
- Mean LVOT gradient (MGV1) by PW Doppler
- Doppler Velocity Index (DVI) =  $VTI_{LVOT} / VTI_{Ao}$
- Grade of aortic transvalvular regurgitation
- Grade of aortic paravalvular regurgitation
- Grade of mitral regurgitation
- PISA for MR (optional)
- Max tricuspid regurgitant (TR) jet velocity (if TR is present)
- Left ventricular (LV) end-diastolic diameter (LVEDD)
- Left ventricular (LV) end-systolic diameter (LVESD)
- Interventricular septal thickness at end diastole
- Left ventricular posterior wall thickness at end diastole
- Left atrial diameter (AP linear dimension) at end systole
- Left ventricular ejection fraction by visual estimate
- Heart rate from Doppler signal
- Mitral inflow "A" velocity
- Mitral inflow "E" velocity
- Mitral inflow E-wave deceleration time
- Mitral annular tissue Doppler systolic velocity (septal and lateral)
- Mitral annular tissue Doppler early diastolic velocity (septal and lateral)
- Mitral annular tissue Doppler late diastolic velocity (septal and lateral)

Procedures for acquiring aortic root measurements and key hemodynamic variables are described in the following sections. For Doppler velocities, the values reported should represent the average of measurements from at least three cardiac cycles for patients in sinus rhythm, and the average of measurements from five cardiac cycles for patients not in sinus rhythm. For aortic valve, TR jet, and tissue Doppler velocities, the reported values should represent the average of the highest velocities obtained from the same transducer position.

\* Screening/baseline measurements should be noted on the echo submitted for Screening Committee review.

**5. Table 1. list of echo recordings (views)**

- Please include all LV walls including epicardium are within the scan sector
- Please enter patient's height, weight, and blood pressure during echo acquisition
- Please optimize frame rate of 2D colour Doppler around 20 Hz if possible
- Shift the colour flow zero baseline downwards or upwards in the regurgitant jet direction in the left PLAX view depending on the jet orientation and upwards in the apical view
- Record frozen images & cine loops in the following order:

**A: From parasternal long-axis window**

1. 2D greyscale standard view
2. 2D Colour Doppler of mitral regurgitation (MR)
3. 2D Colour Doppler of aortic (or prosthetic) regurgitation (AR)
4. If AR is present, **ZOOM** & narrow sector with focus on vena contracta of regurgitant jet
5. If AR is present, **ZOOM** & narrow sector, shift Nyquist 35-40 for PISA measurements
6. 2D greyscale **ZOOM** for LV outflow tract diameter (LVOT) (**3 recordings**)
7. 2D greyscale **ZOOM** at an intercostal space higher for aortic root / aortic prosthesis

**B: From parasternal short-axis window (use same depth setting)**

8. 2D greyscale LV at mitral valve level
9. 2D greyscale LV at papillary muscle level
10. 2D greyscale-guided M-mode at LV minor axis (LV dimensions, avoid papillary muscles)
11. 2D greyscale LV at apical level: *lower your transducer position by 1 or 2 intercostal spaces and record the LV as circular as possible, just proximal to the level with end-systolic LV luminal obliteration*
12. 2D greyscale aortic valve level (post TAVI the native annulus is usually identified by maximal calcification)
13. 2D greyscale-guided M-mode of left atrial & aortic dimensions
14. 2D Colour Doppler of AR: *in post-TAVI start scanning from highest position and record first visible AR jet, scan more downwards and try to pick up additional jets – confirm origin of AR jets from PLAX*
15. 2D greyscale **ZOOM** & focussed on RV outflow tract (RVOT) – pulmonic valve should be visible
16. 2D Colour Doppler of pulmonary regurgitation (PR)
17. If PR is present, CWD of PR jet (include both systolic & diastolic signals)
18. PWD of RVOT velocity (within 0.5 -1cm below the pulmonic valve) (frozen image)

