where  $\pi_{TAVI}$  and  $\pi_{SAVR}$  denote the proportion of subjects with moderate/severe aortic insufficiency at the discharge echo. The posterior probability  $P(H | \text{data})$  will be calculated and compared to a threshold of 0.975. The statistical method will be the Bayesian version of a comparison of proportions (see Section C.11).

18. New pacemaker implant rate for TAVI at 30 days or hospital discharge, whichever is longer (secondary objective #7). The hypothesis of interest is

$$H: \pi_{TAVI} < 30\%$$

where  $\pi_{TAVI}$  denote the binary rate of new pacemaker implants for TAVI at 30 days or hospital discharge (if longer). The posterior probability  $P(H | \text{data})$  will be calculated and compared to a threshold of 0.975. The statistical method will be the Bayesian version of a comparison of proportions (see Section C.11).

Other than the hierarchical testing procedure described above, no further multiplicity adjustments will be made in the analyses of the secondary endpoints. Summary data from other secondary objectives, such as device success and procedural success from secondary objectives #20 and #21, respectively, may be provided in the device labeling. However, no claims of statistical significance or other statistical inference will be made.

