#### 7.10 Special considerations for aortic regurgitation by colour flow imaging

In addition to the abovementioned recommendations:

- Standardize the machine settings for all examinations. Keep the Frame Rate around 20 Hz when recording colour Doppler aortic regurgitation
- Colour gain should be set step by step just below the appearance of colour noise artefacts
- For Vena contracta: use a parasternal long-axis view in ZOOM mode with minimal colour sector size and imaging depth to maximize lateral and temporal resolution
- For PISA: Shift the colour flow zero baseline downwards or upwards in the regurgitant jet direction in the left PLAX view depending on the jet orientation and upwards in the apical view)

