**Note: Velocity tracings should be noted on images submitted for Screening Committee review**

**Note: Fine linear signals at peak velocity should not be included in the velocity tracings!**

## 12. Assessment of Aortic Regurgitation

- **Use all echo modalities:** An integrated exam approach using colour flow, pulsed-wave (PW), and continuous-wave (CW) Doppler is used to assess the severity of transvalvular and paravalvular regurgitation.
- **Use four views:** Colour flow Doppler imaging should be performed from the parasternal long and short-axis views, and the apical long-axis and apical 5-chamber views. A recording of the aortic regurgitant signal should be obtained with CW Doppler. If the degree of aortic regurgitation appears more than mild by visual estimate, the velocity in the proximal descending aorta and the abdominal aorta should be recorded with PW Doppler.
- **Severity:** The degree of transvalvular and paravalvular AR will be graded as none, trace, mild, moderate, and severe based on the analysis of the parameters shown in Table 2a.
  - The category of “trace” is used in cases where regurgitation is barely detectable by colour Doppler.
  - Regurgitant signals observed to originate within the stent will be considered transvalvular, and regurgitant signals observed to originate outside the stent will be considered paravalvular.
- Paravalvular regurgitant jets will be characterized by the extent of the aortic regurgitant jet relative to the short axis circumference of the aortic valve (Table 2a- Valve Academic Research Consortium (VARC) Consensus Report for Transcatheter Aortic Valve Implantation (TAVI) and Table 2b. Updated standardized endpoint definitions for transcatheter aortic valve implantation: the VARC-2 consensus document, and Table 3a and b -2008 Focused Update Incorporated Into the ACC/AHA 2006 Guidelines for the Management of Patients With Valvular Heart Disease (published in the October 2008 issues of Journal of the American College of Cardiology and Circulation).

**Table 2a.** Parameters for evaluation of the severity of aortic regurgitation

Prosthetic Aortic Valve Regurgitation Criteria (Central and Paravalvular)			
Parameter	Mild	Moderate	Severe
Valve Structure and Motion Mechanical or bioprosthesis	Usually normal	Usually abnormal†	Usually abnormal†

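### The echo manual orders a short-axis sweep for additional regurgitation jets only after TAVI, so regurgitation may be ascertained unequally between arms, to TAVI's disadvantage and by an unknown amount

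*Combined protocol and SAP*

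**What the plan says.** **Acquisition.** Appendix R.7, section 5 (Table 1), block B, item 14 asks for short-axis colour Doppler of aortic regurgitation (AR). Its technique note is addressed to one arm: "in post-TAVI start scanning from highest position and record first visible AR jet, scan more downwards and try to pick up additional jets". The note ends by asking that jet origin be confirmed in the parasternal long axis. Rule #1 in R.7 section 3 requires strict adherence to the number and order "of recordings as listed on the Table".

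**Grading.** R.7 section 12 states: "Paravalvular regurgitant jets will be characterized by the extent of the aortic regurgitant jet relative to the short axis circumference of the aortic valve". Tables 2a and 2b in that section both include circumferential extent, with mild set below 10% and moderate starting at 10%. The same section also says: "An integrated exam approach using colour flow, pulsed-wave (PW), and continuous-wave (CW) Doppler is used to assess the severity of transvalvular and paravalvular regurgitation".

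**Use of the grade.** Section C.6.8.1 compares the degree of prosthetic regurgitation between arms (endpoint 12). It includes moderate or severe regurgitation in the valve-dysfunction component of endpoints 5 and 6. Section C.6.10.1, claim #17, tests whether TAVI has the lower value of "the proportion of subjects with moderate/severe aortic insufficiency at the discharge echo", against a posterior threshold of 0.975.

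**The concern.** A between-arm comparison of regurgitation needs the same search in both arms. Here the sonographer is told to sweep for further jets after TAVI but receives no such instruction after SAVR, in the view from which circumferential extent is read. Reading by a core laboratory (C.4.10) does not remove the difference, because the laboratory can grade only what the site recorded.

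The protocol gives no reason for limiting the sweep to TAVI. It accepts that paravalvular leak occurs after surgery too: the intraoperative TEE guidance in C.4.7.2 asks for it to be assessed. Elsewhere the recording list is worded for any valve. Item 3 (long-axis colour) covers native and prosthetic valves alike.

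At stake are the description of valve performance in endpoint 12, part of composites 5 and 6, and the power of claim #17. Under the ordered testing in C.6.10, failure on #17 also stops #18.

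**Working it through.** The plan gives no AR rate, no power for claim #17 and no detection rate for the sweep, so there is no plan figure to reproduce. The check is a comparison of texts, followed by an illustration on stated assumptions.

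**Step 1. What differs by arm and what does not (R.7).**

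| Element | TAVI | SAVR |
|---|---|---|
| Long-axis colour AR, vena contracta, PISA (block A) | yes | yes |
| Short-axis colour AR (item 14) | yes | yes |
| High-to-low sweep for more jets, origin confirmed in long axis (item 14 note) | yes | not stated |
| Apical 5- and 3-chamber colour, PISA, CW (blocks E, G) | yes | yes |
| Descending and abdominal aortic flow (block H) | yes | yes |
| Machine settings (section 7.10): "Standardize the machine settings for all examinations" | yes | yes |

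Section 12 sets the four required views without restriction by arm: "Colour flow Doppler imaging should be performed from the parasternal long and short-axis views, and the apical long-axis and apical 5-chamber views". The difference is therefore one added instruction within one of four colour views.

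**Step 2. Direction.** If the sweep finds more jets, it raises the recorded TAVI rate relative to SAVR. The long-axis confirmation could remove some misattributed jets, so the net effect may be smaller than the search instruction alone suggests.

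**Step 3. Which analyses can move.** Endpoint 12 compares degree, so a jet that shifts a grade by one category anywhere on the scale counts. Claim #17 and the AR component of endpoints 5 and 6 move only when a grade crosses into moderate or severe.

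**Step 4. Size of a recorded difference with equal true rates.** If the true rate is p in both arms and SAVR detects a fraction d of what TAVI detects, the recorded excess is p × (1 − d). The values of p and d are assumptions. With p = 3% and d = 0.9 to 0.7, the excess is 3% × 0.1 to 3% × 0.3, or 0.3 to 0.9 points. With p = 30% for any jet of mild grade or worse, it is 3 to 9 points.

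**Step 5. Effect on claim #17.** With x events in n subjects and the Beta(1,1) prior, the posterior mean is m = (x+1)/(n+2) and the variance is v = m(1−m)/(n+3). By normal approximation, P(H | data) = Φ[(m_SAVR − m_TAVI)/√(v_SAVR + v_TAVI)], and success requires more than 0.975. I took n = 800 per arm (half of the 1600 mITT subjects in C.6.5.2) and 200,000 simulated trials per scenario. The recorded TAVI rate equals the true rate times k. In ratio terms, k = 1.1 and 1.25 correspond to SAVR detection of 1/1.1 = 91% and 1/1.25 = 80% of TAVI detection.

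Chance of declaring claim #17:

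| Assumed true SAVR rate | Assumed true TAVI rate | k = 1 | k = 1.1 | k = 1.25 |
|---|---|---|---|---|
| 1% | 1% | 0.018 | 0.012 | 0.005 |
| 3% | 3% | 0.023 | 0.009 | 0.002 |
| 5% | 5% | 0.024 | 0.008 | 0.001 |
| 1% | 0.5% | 0.15 | 0.13 | 0.09 |
| 3% | 1.5% | 0.51 | 0.42 | 0.29 |
| 5% | 2.5% | 0.75 | 0.64 | 0.47 |

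The first three rows are false claims and they become rarer. The last three are true successes and they also become rarer. With 700 per arm the pattern is the same. In a second scenario, with true rates of 2% (TAVI) and 4.5% (SAVR) and SAVR detection of 100%, 90%, 80% and 70%, power is 81%, 67%, 48% and 29%.

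**The case against.** **Grading does not rest on this view.** It integrates colour, pulsed-wave and continuous-wave Doppler, and most of that acquisition is common to both arms. The footnote to the VARC-2 table cautions that circumferential extent is poorly validated and can overstate severity. Rule #1 does not forbid a sonographer from scanning through the short axis after SAVR. All of this stands, and it limits how far the sweep can move a grade.

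**There is a plausible device reason.** The transcatheter frame has several levels, and section 12 requires deciding whether a jet arises inside or outside the stent. Other items in the list also carry TAVI-specific notes for finding the right plane. This may explain why the note was written. It does not show that SAVR receives an equivalent search.

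**Stronger readings that a reader might infer.** One is that the comparison is biased as a matter of fact. The documents do not support that: no figure says how often the sweep changes a grade. Another is that the asymmetry could produce a false labeling claim. It cannot, because claim #17 is a TAVI superiority test and the added search raises the recorded TAVI rate. A third is that large discrepancies in any-grade jets, such as the 3 to 9 points in step 4, carry over to the labeling tests. They do not, because claim #17 counts only moderate or severe AR and the comparison of degree lies outside the hierarchy in C.6.10. The consequence for #18 is also remote, since #17 is reached only after the preceding tests have all succeeded.

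**Unseen text.** Only part of the document is available, and R.7 breaks off at section 17. A SAVR-specific or core-laboratory instruction elsewhere cannot be excluded.

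**Conclusion.** The point holds as a risk of unequal ascertainment, unfavourable to TAVI and of unknown size. It rests on three textual facts: the sweep is written for post-TAVI exams only, short-axis extent is one of the parameters for paravalvular grade, and that grade is compared between arms.

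Endpoint 12 is most exposed. Claim #17 and endpoints 5 and 6 are affected only if extra jets change the grade to moderate or severe. For claim #17 the consequence is possible loss of power, without any increase in false claims. Every AR rate and detection factor in the working is an assumption, so the tables show direction and sensitivity and do not estimate what happened in this trial. The change is worth making because it is cheap and because sweeps not recorded after SAVR cannot be recovered later.

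**What to change.** Reword item 14 so that the short-axis sweep, with long-axis confirmation of jet origin, applies to every post-implant echo in both arms. Have the core laboratory grade circumferential extent from that sweep in both arms. If the sponsor regards the sweep as specific to the transcatheter frame, R.7 should say why and state what equivalent search a surgical valve receives.

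The cost is a one-line change to R.7 and a slightly longer SAVR echo at visits already scheduled. The main drawback is that SAVR exams before and after the change will differ: the sample-size section already cites 654 enrolled subjects, and discharge echoes already acquired cannot be repeated. The report should therefore give the date of the change, summarise AR by arm before and after it, and state that any earlier imbalance would have worked against TAVI. The TAVI instruction does not change, so the TAVI arm gives a reference for drift over calendar time.
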